13. STATISTICAL ANALYSIS PLAN

13.1 Efficacy

13.1.1 ORR

The intention to treat (ITT) population included all patients who received at least one dose of any study treatment. ORR was calculated with two-sided 95% confidence intervals for the overall population. ORR was defined as (CR + PR)/(number of ITT population).

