Method for Assessment:	
1. Efficacy assessment
 
Objective Response Rate (ORR) : The proportion of the patients who have achieved complete response (CR) or partial response (PR) with confirmation. (Tumor response will be evaluated according to RECIST Ver. 1.1)
 
CT or MRI scans of the chest, abdomen, and pelvis, the tumor burden assessment method used at baseline, should also be used for each subsequent follow-up assessment.
 
If a patient discontinues treatment prior to progression (and/or is receiving follow-up cancer treatment), the patients' follow up monitoring should be continued until objective disease progression as defined by RECIST 1.1.
 
Categorization of objective tumor response assessments will be based on the modified RECIST 1.1 response criteria: CR (complete response), PR (partial response), SD (stable lesion), and PD (disease progression).
 
The progression of the target lesion (TL) is calculated compared to when the tumor burden was at a minimal level (ie, the minimum sum of diameters previously recorded during the trial). If not advanced, tumor response (CR, PR, SD) is calculated compared to baseline tumor measurements obtained prior to initiation of treatment.

[Type here]

[Type here]

[Type here]

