6.1 Inclusion Criteria

Each patient must meet the following criteria to be enrolled in this study:

1. The patient is ≥ 18 years of age.
2. The patient who has received an adequate information and provided informed consent for all the study-specific procedures in advance
3. The patient has histologically or cytologically confirmed gastric carcinoma, including gastric adenocarcinoma or GEJ adenocarcinoma. (Patients with adenocarcinoma of the distal esophagus are eligible if the primary tumor involves the GEJ.) patient has metastatic disease or locally recurrent,

[Type here]

[Type here]

[Type here]

Pembrolizumab + Ramucirumab (Ver 2.5, Oct 2024)

unresectable disease.

4. The patient's tumor tissue must have the pre-defined characteristics as follows ;
EBV+ or PDL1 CPS \geq 5
5. The patient has measureable or evaluable disease as determined by standard computed tomography (CT) or magnetic resonance imaging (MRI) imaging. Examples of evaluable, nonmeasurable disease include gastric, peritoneal, or mesenteric thickening in areas of known disease, or peritoneal nodules that are too small to be considered measurable by Response Evaluation Criteria in Solid Tumors (RECIST version 1.1)
6. The patient has experienced disease progression during first-line treatment or second-line therapy for metastatic disease.
 - Acceptable prior chemotherapy regimens for this protocol are combination chemotherapy regimens that include platinum and/or fluoropyrimidine components (acceptable prior platinum agents are cisplatin, carboplatin, or oxaliplatin; acceptable prior fluoropyrimidine agents are 5-FU, capecitabine, or S-1). Regimens including a third agent, such as an anthracycline or a taxane, are acceptable provided a fluoropyrimidine and/or a platinum were used.
 - Recurrence during or within 6 months of completion of adjuvant chemotherapy (capecitabine, 5-FU, or TS-1) will be considered as first-line chemotherapy.
7. No prior exposure to anti-PD1 antibody or ramucirumab. Or ramucirumab can participate if the investigator determines that there is a clinical benefit.
8. The patient has an Eastern Cooperative Oncology Group performance status (ECOG PS) score of 0 or 1.
9. Patients must have acceptable bone marrow, liver and renal function measured within 28 days prior to administration of study treatment as defined below:
 - ✓ Haemoglobin \geq 9.0 g/dL
 - ✓ Absolute neutrophil count (ANC) $\geq 1.5 \times 10^9$ /L
 - ✓ Platelet count $\geq 100 \times 10^9$ /L

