10.1.1 Tumor Evaluation

Modified RECIST 1.1 criteria will be used to assess patient response to treatment by determining PFS and ORR. The modified RECIST 1.1 guidelines for measurable, non-measurable, target and non-target lesions and the objective tumour response criteria (complete response, partial response, stable disease or progression of disease).

The methods of assessment of tumour burden used at baseline, CT or MRI scans of chest, abdomen and pelvis must be used at each subsequent follow-up assessment.

Following the baseline assessment, efficacy for all patients will be assessed by objective tumour assessments every 6 weeks relative to date of first dose until objective disease progression as defined by modified RECIST 1.1. See Study Schedule (Table 1) for further details.

[Type here]

[Type here]

[Type here]

Pembrolizumab + Ramucirumab (Ver 2.5, Oct 2024)

If a patient discontinues treatment (and/or receives a subsequent cancer therapy) prior to progression then the patient should still continue to be followed until objective disease progression as defined by modified RECIST 1.1.

Categorisation of objective tumour response assessment will be based on the modified RECIST 1.1 criteria of response: CR (complete response), PR (partial response), SD (stable disease) and PD (progression of disease). Target lesion (TL) progression will be calculated in comparison to when the tumour burden was at a minimum (i.e. smallest sum of diameters previously recorded on study). In the absence of progression, tumour response (CR, PR, SD) will be calculated in comparison to the baseline tumour measurements obtained before starting treatment.

For patients with non-measurable disease only at baseline, categorisation of objective tumor response assessment will be based on the modified RECIST 1.1 criteria of response: CR, PD and Non CR/Non PD.

If the investigator is in doubt as to whether progression has occurred, particularly with response to NTL (non-target lesion) or the appearance of a new lesion, it is advisable to continue treatment until the next scheduled assessment or sooner if clinically indicated and reassess the patient's status. If repeat scans confirm progression, then the date of the initial scan should be declared as the date of progression.

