12. SAMPLE SIZE

Sample Size Calculation

[Type here]

[Type here]

[Type here]

Pembrolizumab + Ramucirumab(Ver 2.5, Oct 2024)

A maximum of 26 patients will be recruited to this single-arm phase II trial. The primary endpoint of this trial is overall response (OR=PR+CR).

In this single-arm phase II trial, 25 people were calculated using Simon's two-stage design and a total of 26 patients will be recruited to account for a 5% dropout rate.

The sample size is calculated by use of a two-stage minimax Simon's design to control the type I error at 5 % for null hypothesis that, for arm, the true response was 15 % or below and to have 85 % of power if the true response was 40 % or higher. 15 evaluable patients are to be treated in the first stage. If 1 or fewer response are observed in the first stage, the arm will be stopped. If at least 2 responses are observed in the first stage, 10 additional evaluable patients are to be entered onto the second stage. At the final analysis, the null hypothesis will be rejected if at least 7 responses are observed in 25 evaluable patients. RR is reported with its exact 95% CI.

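### The primary ORR is not defined once: the decision rule, the SAP formula and the synopsis differ on denominator and confirmation, and the cutoff of 7 does not hold 5% in either denominator.

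*Combined protocol and SAP*

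**What the plan says.** **Decision rule (Section 12, repeated in the synopsis).** The design is meant "to control the type I error at 5" percent under the null that "the true response was 15 % or below", and "to have 85 % of power if the true response was 40 % or higher". The rule is stated for evaluable patients: "15 evaluable patients are to be treated in the first stage", the arm stops with 1 or fewer responses, 10 more evaluable patients follow, and the null is rejected with 7 or more responses in 25. Recruitment is capped at 26 to cover 5% dropout. No section says what makes a patient evaluable.

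**SAP formula (Section 13.1.1).** "ORR was defined as (CR + PR)/(number of ITT population". The set called ITT is everyone given any study drug.

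**Confirmation.** The synopsis (Method for Assessment) counts patients "who have achieved complete response (CR) or partial response (PR) with confirmation". It lists BORR separately as a secondary endpoint that needs only a single CR or PR. Sections 5.1, 10.1.1, 12 and 13.1.1 do not mention confirmation of response. The repeat scan in Section 10.1.1 concerns doubtful progression.

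**Measurability.** Inclusion criterion 5 (Section 6.1) reads "The patient has measureable or evaluable disease as determined by standard computed tomography (CT", and its examples of evaluable disease are non-measurable. For patients with only such disease, Section 10.1.1 allows the "criteria of response: CR, PD and Non CR/Non PD". PR is not among these categories.

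**The concern.** The trial's conclusion rests on one integer threshold in about 25 patients, so the plan must fix who is counted and what counts as a response. It leaves three things open:

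- **Denominator.** A patient who is dosed but never scanned is a non-responder under Section 13.1.1 and may be left out under Section 12.
- **Numerator.** A single unconfirmed PR is a response under the SAP formula and is not one under the synopsis.
- **Dilution.** Patients who can respond only by CR may sit in either set, although the 40% target makes no allowance for them.

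The trial is open-label and single-centre. If these choices stay open, they can be made after the responses are known.

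**Working it through.** **Inputs.** From Section 12: null rate 15%, target rate 40%, stage 1 of 15 patients, stop at 1 or fewer responses, total 25, success at 7 or more, recruitment cap 26. The shares of unscanned patients, non-measurable patients and unconfirmed responses are not in the documents; values used for them below are assumptions.

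**Formula.** For total n, success cutoff k and true rate p,

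P(success) = Σ over x = 2 to 15 of P[Bin(15, p) = x] × P[Bin(n − 15, p) ≥ k − x].

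**Step 1: the plan's own figures (n = 25, k = 7).** At p = 0.15 the result is 6.9%, against 5% stated. At p = 0.40 it is 92.6%, against 85% stated. Neither is reproduced.

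**Step 2: one treated patient dropped.** With a cap of 26 and 25 evaluable, at most 1 of 26 (3.8%) can be dropped. If that patient is a non-responder, a true all-treated rate of 15% becomes 0.15 × 26/25 = 15.6% among the evaluable. At p = 0.156 the 7-of-25 rule succeeds with probability 8.2%.

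**Step 3: all 26 treated, as in Section 13.1.1.**

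| n | Cutoff | Type I error (p = 15%) | Power (p = 40%) |
|---|---|---|---|
| 25 | 7 | 6.9% | 92.6% |
| 26 | 7 | 8.3% | 94.3% |
| 25 | 8 | 2.5% | 84.6% |
| 26 | 8 | 3.2% | 87.8% |

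A cutoff of 7 exceeds 5% in both sets, and a cutoff of 8 holds it in both. With 7 responders, the reported ORR is 7/25 = 28.0% (exact 95% CI 12.1–49.4) or 7/26 = 26.9% (11.6–47.8).

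**Step 4: non-measurable disease.** Assume that a share f has only non-measurable disease with no CRs, and that the true rate in the others is 40%. The overall rate is then 0.40 × (1 − f). Under the stated 7-of-25 rule:

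- f = 0: rate 40%, power 92.6%
- f = 10%: rate 36%, power 85.1%
- f = 20%: rate 32%, power 73.3%

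**Step 5: confirmation.** Assume that the confirmed rate is 15% and that counting unconfirmed responses adds 3 to 5 points, giving 18% to 20%. The chance of success under the 7-of-25 rule rises from 6.9% to between 14.8% and 21.9%.

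**The case against.** **The denominator rarely changes the decision.** The rule is a count of responses. A dosed patient with no scan adds none, so with 26 treated and 25 evaluable the final count is the same in both sets. This stands. What remains open is who makes up the first 15, and whether a 26th patient's response counts if all 26 can be assessed.

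**Evaluable might mean treated.** The plan defines enrolment as assignment to treatment, so drop-outs could be patients who were never dosed. Sections 12 and 13.1.1 would then agree. This is possible, but the plan does not say it.

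**A reader might infer much larger inflation.** Dropping 10% or 20% of treated patients would take the null rate to 16.7% or 18.75%, and the type I error of the 7-of-25 rule to 10.9% or 17.3%. Section 12 does not support this. To keep 25 evaluable would need 25/0.9 = 27.8 (28) or 25/0.8 = 31.25 (32) treated patients, and the cap is 26. Section 7.1 does give a maximum of 35, but that conflicts with Section 12 and has to be reconciled separately.

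**Confirmation is silence, not contradiction.** The synopsis requires it and sets ORR apart from BORR, so confirmed response is probably intended. That is the fair reading. But the formula that will be programmed is the one in Section 13.1.1, and it lacks the word.

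**Non-measurable patients.** A reader might infer that both sets certainly include them, or that they can never be responders. Neither follows. The evaluable set is undefined, the number enrolled is unknown, and CR is open to them. Similarly, the DCR definition does not say how non-CR/non-PD is counted, so treating it as failure is only a literal reading.

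**Conclusion.** The concern holds at a moderate size. The plan leaves the primary ORR open on its analysis set and, in the SAP formula, on confirmation.

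The denominator question alone moves the type I error of the 7-response rule from 6.9% to 8.2% or 8.3%, assuming the 26-patient cap holds. The excess of 6.9% over 5% comes from the cutoff itself and would remain if the sets were harmonised. The two matters belong together because any agreed set needs a cutoff that works in it.

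Confirmation is the element most able to change the result, since it alters the count; its size depends on an unconfirmed share that the documents do not give. The power loss from non-measurable disease is likewise conditional. At 10% with no CRs the stated rule still gives 85.1%, which meets the 85% target; at 20% it gives 73.3%, which does not.

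**What to change.** Put one definition in the synopsis, Section 12 and Section 13.1.1:

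- **Set:** every patient who received any study drug, called 'all treated' rather than ITT.
- **Response:** confirmed CR or PR by the response criteria the plan already uses.
- **No post-baseline scan:** non-responder, not replaced.
- **Decision rule:** both Simon looks applied to this set in order of enrolment, the stage 1 rule unchanged, success at 8 or more responses whether 25 or 26 are treated.
- **Sensitivity analysis:** ORR in patients with measurable disease at baseline. Restricting the primary set to them is not needed and could break the 26-patient cap.
- **DCR:** state that non-CR/non-PD counts as disease control.

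**Cost.** Protocol and SAP wording only; the six-weekly scans already scheduled can serve for confirmation. The reported ORR will be slightly less favourable, and at 25 patients power is 84.6% rather than 85%. The higher cutoff also leaves less reserve against dilution: under the same assumption of 10–20% non-measurable disease with no CRs, power of 8 of 25 would be 72.9–57.4%. The sponsor should accept that knowingly.

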13.1.2 Biomarker

To explore and identify biomarkers (inform the scientific understanding of diseases and/or their therapeutic treatment), the contingency tables will be presented by response for each of tumor histology, molecular signatures, immune pathways and etc..

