	
For patients with only non-measurable disease from at baseline, categorization of objective tumor response assessment will be based on the modified RECIST 1.1 response criteria: CR, PD, non-CR/non-PD.
 
If the investigator is not sure whether progression has occurred, especially if there is a reaction to a non-target lesion (NTL) or a new lesion develops, if clinically necessary, dosing can be continued before next scheduled visit and be advisable to re-evaluate the patient's condition.
 
If progress is confirmed in the repeat scan, the progress date should be declared as the first scan date.
 
Secondary efficacy assessment will be conducted as follows:
 
 Best Overall Response Rate (BORR) is defined as the proportion of the patients who have achieved CR or PR at least once. Disease Control Rate (DCR) is defined as the proportion of the patients with a documented CR, PR, and SD (results will be provided by confirmed and unconfirmed). Progression-Free Survival (PFS) is defined as the time from first administration of investigational drug to the earlier date of PD or death due to any cause. Overall Survival (OS) is defined as the time from first administration of investigational drug to death due to any cause. Duration of Overall Response (DOR) is defined as the time from the first date of assessment as CR or PR to the earlier date of PD or death due to any cause. Maximal Tumor Shrinkage(MTS) is defined as rate of change in tumor size relative to the baseline at the time of best improvement. 
2. Safety assessment
 
The severity of all AEs will be graded for laboratory toxicity and symptoms according to NCI-CTCAE Ver. 5.0. For the events that are not pre-defined in terms under NCI-CTCAE, Investigator should assign a numeric grade of “1” to “5” using the definitions as Mild, Moderate, Severe, Life-threatening, Death, respectively based on maximal intensity.
 
3. Biomarker assessment
 
To collect and store diagnostic and/or archival tumour samples and any fresh tumour biopsies (pre-treatment if clinically feasible and before 3 cycles if clinically feasible) for potential future exploratory research into factors that may influence development and/or response to ramucirumab in combination with pembrolizumab. Next generation sequencing from these samples and/or other protein based exploratory analysis will be carried out. Fresh tissues at baseline is required if clinically feasible

--	---

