5.0 Objective

5.1 Primary Objective:

To estimate preliminary overall response rate (ORR) of combination therapy of Ramucirumab and Pembrolizumab in patients with metastatic gastric or GEJ adenocarcinoma

5.2 Secondary Objectives:

To assess secondary measures of clinical efficacy

- Best Overall Response Rate:BORR

[Type here]

[Type here]

[Type here]

Pembrolizumab + Ramucirumab (Ver 2.5, Oct 2024)

- Disease Control Rate: DCR
- Progression-Free Survival: PFS
- Overall Survival: OS
- Duration of Overall Response: DOR & maximal tumor shrinkage

5.3 Biomarker Objectives:

Integrative immune-genomic analysis to identify association of response with prevalent markers (e.g. PD-L1 expression, EMT signature, T-cell and cytolytic immune signatures, RNA-seq, hypermutation, pre and post cfDNA cancer panel genomics (Changes of TMB and landscape of genome), PFS/OS/safety

- ✓ Fresh tissues at baseline pre-treatment if clinically feasible and before 3 cycles if clinically feasible)
- ✓ (archival tissue only is not acceptable for study entry due to limited analysis on archival tissues)
- ✓ RNA sequencing to understand the mechanism of action of pembrolizumab and ramucirumab in responders and non-responders.
- ✓ Evaluating changes of component of Immune cells and cytokines in blood
- ✓ Describe the association between EBV gastric cancer /or MSI and clinical activity in subjects who metastatic gastric or GEJ adenocarcinoma.

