7. CARE PLAN

7.1 Study Design and Plan

This study is a single arm, open label, single center phase II study of ramucirumab in combination with pembrolizumab in EBV+ or CPS≥5 patients with advanced gastric adenocarcinoma including gastric adenocarcinoma or GEJ adenocarcinoma as a second or third line chemotherapy

[figure not shown]
Patients will receive ramucirumab plus pembrolizumab combination regimen. This study recruits a maximum of 35 patients.

Lilly will only supply ramucirumab and Merck will supply pembrolizumab. Lilly and Merck will not supply other medications used in the care of patients while on this study.

Patients will receive ramucirumab, administered via intravenous (I.V.) infusion over approximately 1 hour, every 2 weeks, at a dose of 8 mg/kg, and pembrolizumab 200 mg will be administered as a 30 minute IV infusion every 3 weeks. (pembrolizumab first followed by

[Type here] [Type here] [Type here]

Pembrolizumab + Ramucirumab(Ver 2.5, Oct 2024)
ramucirumab when concurrently administered on the same day)
- Ramucirumab 8mg/kg on q2W
- Pembrolizumab 200mg on q3W

Assessment of disease control is recommended every 6 weeks (every cycle).

It is recognized that in the course of clinical cancer care, it is not always possible to schedule therapeutic infusions precisely 2 weeks-ramucirumab/3 weeks-pembrolizumab following a prior infusion (because of holidays, travel difficulties, or other circumstances). Accordingly, infusions administered within 3 days before or after the planned time point are acceptable. Administration beyond this window is strongly discouraged.

All patients may continue to receive treatment with the IP, ramucirumab, until there is evidence of progressive disease (PD), unacceptable toxicity, the patient is withdrawn from the study for any other reason, or ramucirumab becomes commercially available and accessible to patients after local marketing authorization. Also, if ramucirumab stops then pembrolizumab be discontinued as well.

Treatment may be discontinued as outlined in Section 6.3

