7.2 Enrollment/screening Period

The following assessments and procedures should be performed within 28 days prior to first dose of study treatment. For details of the schedule and nature of the assessments, see below.

- Signed informed consent for the study; include main inform consent
- Results of EBV IHC or PDL1 (EBV positive or PDL1 CPS≥5)

EBV test: (all centralized at CAP-certified pathology lab/SMC): he entire procedure was performed on a fully automatic system (BOND-MAX) for in situ hybridization with an EBV-encoded RNA probe from Leica (Newcastle, UK) following manufacturer's instructions (ref: Gastroenterology [Type here] [Type here] [Type here])

Pembrolizumab + Ramucirumab (Ver 2.5, Oct 2024)
2010 vol 139, pages 84-92).

PDL1 test: IHC staining will be carried out on Dako Autostainer Link 48 system (Agilent Technologies, Santa Clara, CA) using Dako PD-L1 IHC 22C3 pharmDx kit (Agilent Technologies) with EnVision FLEX visualization system and counterstained with hematoxylin according to the manufacturer's instructions. PD-L1 protein expression will be determined by using Combined Positive Score (CPS), which was the number of PD-L1 staining cells (tumor cells, lymphocytes, macrophages) divided by the total number of viable tumor cells, multiplied by 100. (ref: https://www.agilent.com/cs/library/usermanuals/public/29158_pd-l1-ihc-22C3-pharmdx-nslcl-interpretation-manual.pdf)

- Date of birth, race and ethnicity
- Medical and surgical history
- Current and concomitant medications including previous cancer therapies (if applicable)
- Physical examination
- ECOG performance status
- Vital signs (blood pressure, pulse and body temperature), body weight and height.
- Hematology, clinical chemistry and urinalysis, TFT
- Menopausal status; serum or urine pregnancy test for women of childbearing potential (within 7 days prior to study treatment start
- ECG
- Echocardiogram/MUGA Should be completed if patients had received prior anthracycline therapy
- Tumor assessment (scans of the abdomen/pelvis/other sites as clinically indicated for assessment of disease [CT/MRI]), performed within 14 days prior to enrollment, ideally should be performed as close as possible to the start of the treatment. Scans that were performed as part of standard of care prior to signature of the informed consent form can be analysed for the purposes of the study if they were performed within the correct time frame and consistent with modified RECIST guidelines for CT or MRI

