10.3 Biomarker Evaluation

We will conduct Biomarker Research on specimens collected during this clinical trial. This research may include genetic analyses(DNA), gene expression profiling (RNA), proteomics, metabolomics (serum, plasma) and/or the measurement of other analytes.

Genomic analysis: Whole Exome Sequencing at baseline if it is feasible, RNA-seq pre and post (Whole Exome Sequencing/RNA sequencing will be performed at SMC using vendor (Macrogen INC., Korea) and analyzed together with the BI team at SMC with Merck MSD or Lilly.

The objective of collecting specimens for Biomarker Research is to explore and identify biomarkers that inform the scientific understanding of diseases and/or their therapeutic treatments. Integrative genomic analysis (i.e. gene signature, etc.) measured may be a predictive biomarker for patients who receive pembrolizumab treatment.

Integrative immune-genomic analysis to identify association of response with prevalent markers (e.g. PD-L1 expression, EMT signature, T-cell and cytolytic immune signatures, RNA-seq, hypermutation, cfDNA cancer panel genomics).

Pre and post (on-drug biopsy at 6 weeks): RNA sequencing and cfDNA cancer panel genomics to understand the mechanism of action of pembrolizumab/ramucirumab in responders and non-responders.

Pre and post (at baseline, at 3-week and at 6-week post-treatment) to evaluating immune-priming effect of chemotherapy alone and pembrolizumab:

- i) The assessment of plasma or cell free tumor DNA (ctDNA) variant allele frequency (VAF) and tumor mutation burden (TMB) at baseline, at 3-week and at 6-week post-treatment;
- ii) The assessment of integrated molecular profiling (including T cells-

[Type here]

[Type here]

[Type here]

Pembrolizumab + Ramucirumab(Ver 2.5, Oct 2024)

CD3+,CD8+,CD45RO+, Tregs-FOXP3+ and macrophages-CD163+, MHC-1, and PDL1 expression) will be assessed using single cell sequencing (blood and tissue) via 10X genomics.

As an exploratory analysis, we will isolate T cells using FACS sorting and sequence these cells. In addition, in order to identify the relationship between neoantigen drivers like infection and response to pembrolizumab, we will prospectively collect serum antigens from blood at baseline. FACS (Cytex) 20-panel antibody will be used.

11. Adverse Events and Dose Modification

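### The SAP's only biomarker analysis is contingency tables by response, so quantitative markers would need cutpoints it does not give; analyse them uncut and label the results exploratory

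*Combined protocol and SAP*

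**What the plan says.** Section 13.1.2 is a single sentence. Its aim is "To explore and identify biomarkers", and its method is that "the contingency tables will be presented by response for each of tumor histology, molecular signatures, immune pathways and etc". It names no test, significance level, cutpoint or multiplicity rule.

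The objective behind it is an association question. Section 5.3 (and the synopsis) has: "Integrative immune-genomic analysis to identify association of response with prevalent markers (e.g. PD-L1 expression, EMT signature, T-cell and cytolytic immune signatures". Section 10.3 repeats it: "Integrative immune-genomic analysis to identify association of response with prevalent markers".

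Several of the markers are numbers, not categories:

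- **PD-L1 CPS** is a computed score. Section 7.2 defines it as a count of staining cells "divided by the total number of viable tumor cells, multiplied by 100".
- **Plasma DNA** is assessed in Section 10.3 for "variant allele frequency (VAF) and tumor mutation burden (TMB") at baseline, 3 weeks and 6 weeks.
- **Expression signatures** (EMT, T-cell, cytolytic) come from RNA sequencing.

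The only CPS threshold is the entry rule. Section 7.1 describes the trial as being "in EBV+ or CPS≥5 patients". It is not offered as an analysis cut.

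The synopsis also defines a quantitative outcome: "Maximal Tumor Shrinkage(MTS) is defined as rate of change in tumor size relative to the baseline at the time of best improvement". No analysis links it to the markers.

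**The concern.** A contingency table needs categories. Within the one method stated, a CPS, a TMB value, a VAF or a signature score has to be grouped first, and the plan does not say where. Two things follow.

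First, grouping throws away the ordering of patients within each group. With about 25 patients and perhaps 7 to 10 responders, little information can be spared, and a real association becomes easier to miss.

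Second, an open cutpoint can be chosen after the data are seen. The protocol lists many markers, so picking the best-looking cut for each would produce spurious associations. The CPS threshold of 5 does not help: everyone who enters on CPS is already above it, so it can separate only patients admitted on EBV status.

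**Working it through.** **The plan's own figure.** There is none for biomarkers. Section 12 sizes the trial on ORR alone. What follows compares two possible analyses under assumed conditions.

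**Inputs from the plan.** 25 evaluable patients; a 40% response rate under the alternative (25 × 0.40 = 10 responders); at least 7 responses needed for success (7/25 = 28%). All are in Section 12.

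**Assumed inputs.** Two-sided 5% tests. Marker distributed N(0,1) in non-responders and N(d,1) in responders, with d = 0.75, 1.0, 1.25, 1.5. In AUC terms, AUC = Φ(d/√2) = 0.70, 0.76, 0.81, 0.86. The number of responders is Binomial(25, p). The full-scale analysis is the exact Wilcoxon rank-sum test. The table analysis is a 2×2 table split at the sample median, tested by uncorrected chi-square or by Fisher's exact test.

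**Simulated power (%), 5,000 replicates per setting, median patient in the lower group.**

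| Response rate | d | Wilcoxon | Chi-square | Gap | Fisher | Gap |
|---|---|---|---|---|---|---|
| 40% | 0.75 | 37.1 | 27.5 | 9.6 | 26.4 | 10.7 |
| 40% | 1.0 | 59.5 | 44.9 | 14.6 | 43.1 | 16.4 |
| 40% | 1.25 | 78.1 | 62.6 | 15.5 | 60.4 | 17.7 |
| 40% | 1.5 | 90.9 | 77.5 | 13.4 | 75.6 | 15.3 |
| 28% | 0.75 | 30.8 | 25.4 | 5.4 | 20.3 | 10.5 |
| 28% | 1.0 | 50.5 | 39.4 | 11.1 | 32.0 | 18.5 |
| 28% | 1.25 | 69.3 | 54.2 | 15.1 | 47.0 | 22.3 |
| 28% | 1.5 | 83.3 | 67.9 | 15.4 | 60.5 | 22.8 |

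**Placing the median patient.** With 25 patients, one sits on the median. If that patient joins the upper group at 28% response, Fisher power is 16, 27, 38 and 52%, and the gaps against Wilcoxon (31, 51, 69, 83%) become 15, 24, 31 and 31 points. A repeat of all settings with 20,000 replicates agreed within 2 points. It put the chi-square gap at about 8 to 19 points when the median patient joins the upper group.

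**Hand check.** Take 10 responders, 15 non-responders and d = 1. The standard error is √(1/15 + 1/10) = 0.408. Full-scale power ≈ Φ(1/0.408 − 1.96) = Φ(0.49) ≈ 69%. A median split has relative efficiency about 2/π, so power ≈ Φ(√(2/π)/0.408 − 1.96) = Φ(−0.01) ≈ 50%. The gap is about 19 points, the same order as the simulation.

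**Not all of Fisher's gap is lost information.** At 28% response and no true difference, Fisher rejects about 3.1% of the time and Wilcoxon about 4.9%. Chi-square is the fairer measure of what grouping itself costs.

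**Post-hoc cut.** For one marker with no true association (25 patients, 40% response), take the cut that gives the smallest Fisher p-value, with 5 to 20 patients in the lower group. The false-positive rate is about 18% instead of 5%.

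**Smaller samples.** Biopsy may be waived when unsafe or inaccessible, so tissue markers may cover fewer than 25 patients. A stage 1 stop leaves at most 1 responder in 15. Even the most extreme ranking then gives a two-sided exact p of 2/15 = 0.13, so no method could help.

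**The case against.** A reader might infer that the plan requires every continuous marker to be dichotomised, and that it therefore loses a fixed amount of power, say 11 to 23 points. The documents do not support that.

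- Section 13.1.2 does not exclude other analyses, its list is open-ended, and it does not name CPS, TMB or VAF. It does cover molecular signatures. Section 4.4.3 plans a comparison by molecular subtype, for which tables are the natural tool.
- The tables are exploratory. No test is planned, so there is no planned power to lose. Fisher's test, the 5% level, the median split and the effect sizes are all assumptions of this check.
- The size is unstable. Over a wider set of responder counts and shifts (4 to 12 responders, 0.5 to 2.0 SD), the gap between Fisher on a median split and a full-scale t or rank test ran from about −3 to +44 points.
- Section 7.1 gives a maximum of 35 patients against 26 in Section 12, so even the sample size is not settled.
- Adding tests for many markers in 25 patients brings its own false-positive risk.

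These points limit the claim but do not remove it. If Section 13.1.2 does not reach CPS, TMB and VAF, those markers have no stated method at all. If it does reach them, they need cutpoints that are missing. Even as description, an AUC with its interval keeps information that a split table drops. The multiplicity point stands and is built into the fix.

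**Conclusion.** The point holds in a limited form. The only stated biomarker method suits categorical markers. For the quantitative ones it requires a grouping that the plan leaves open, and a full-scale comparison of data already being collected would do better.

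The illustrative cost of a median split against a Wilcoxon test is roughly 5 to 16 points of power with chi-square (up to about 19 if the median patient joins the upper group), and roughly 11 to 31 points with Fisher across both placements. This rests on 25 patients with the marker measured, 28% to 40% response, a normal marker, a shift of 0.75 to 1.5 SD and two-sided 5% tests. Only the sample size and the response rates come from the plan. Fewer evaluable samples would change the figures.

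The primary ORR analysis and the decision rule are untouched. This is a minor improvement worth making because it is cheap.

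**What to change.** Revise Section 13.1.2 as follows.

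- Keep contingency tables by response for categorical markers: histology, EBV status, MSI and molecular subtype.
- For quantitative markers (CPS, TMB, ctDNA VAF and its change, signature scores), compare responders with non-responders uncut. Use the exact Wilcoxon rank-sum test and report the AUC with 95% CI. State which time point is used and how many patients have the marker measured.
- Optionally add the Spearman correlation with maximal tumor shrinkage, restricted to patients with measurable disease, because Section 6.1 also admits non-measurable disease.
- If a grouped display is wanted, write its cutpoint into the SAP before the data are seen.
- Label all biomarker results exploratory. Either state that p-values are unadjusted or control the false discovery rate across markers.

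The cost is a few sentences and minor programming, with no new patients, samples or data. The one drawback is that a rank test with an AUC is slightly harder to read than a 2×2 table, which can still be shown as a descriptive display.
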